1.1 Background

Dentin Hypersensitivity can be defined as “Short acting, sharp pain that arises from exposed dentine due to various stimuli which is evaporative, thermal, osmotic, tactile and chemical and this pain cannot be attributed to any other form of dental defect, disease or pathology ^{1, 2}. Many other terms have been used to diagnose this typical common condition such as Dentine Sensitivity, Root sensitivity, cervical dentine sensitivity, cemental hypersensitivity but Dentin Hypersensitivity is the most often used term across the literature ³.

It has been reported that Dentin Hypersensitivity has multifactorial etiology and patients with periodontal and gingival disease usually encounter this painful condition ⁴. Dentin Hypersensitivity is initiated by denudation of dentinal tubules and several possible common causative factors which include gingival recession, pockets formation, acute and chronic inflammatory periodontal diseases, trauma, traumatic occlusal forces, parafunctional habits, acidic dietary components, abrasion, erosion, attrition, abfraction, tooth flexure, faulty and overzealous tooth brushing and periodontal procedures (specially Scaling and Root planing) lead to dentine exposure ⁵⁻⁷.

Dentin Hypersensitivity as reported by Canadian Advisory Board is Diagnosis of Exclusion ². It is diagnosed by means of self-report of sharp pain in vital tooth/ teeth by patients in response to external stimuli. ⁸.

A number of theories have been put forward to describe the mechanism of Dentin Hypersensitivity ⁹ but Brannstorm’s Hydrodynamic Theory is the most widely acceptable theory

and according to this theory, various stimuli cause changes in fluid movements in dentinal tubules either outwards or inwards, resulting in activation of nociceptors in pulpodentinal border, which ultimately lead to the characteristic short, sharp pain of Dentin Hypersensitivity^{10, 11}.

Variation in Prevalence of Dentin Hypersensitivity exists worldwide, ranging from 1.34% to 98%¹²⁻¹⁴. This presence of variation exists due to several reasons including different study designs, different selection criteria for each study sample, different diagnostic approaches and also type of setting where study was performed^{15, 16}.

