1. Patients with Carious, Cracked or Restored teeth, Abutment teeth used of Removable or Fixed Prosthesis and tooth with any other dental pathology.
2. Patients using analgesics, mood alteration drugs during last six months.
3. Smoker, pregnant and nursing mothers.
4. Patients using tooth whitening or bleaching agents in the last six months,
5. Patients undergoing orthodontic therapy and history of periodontal surgery during last six months.
6. Patients who refuse to give consent.
7. Patients who had Score 2 and 3 of Calculus index will also be excluded from this study.

2.5 Sample Size:

Total 50 patients will be carried out (25 in each group). Using PASS version 11, test for Pair means with 99% Confidence Interval and Power of test, mean difference of degree of sensitivity 1.8 (1.9 – 0.01) ²⁷ and 0.42 of Standard Deviation difference (3.35 – 2.93) ²⁷, sample size is 5 patients per group which we have increased to 25 patients per group.

2.6 Sampling Technique:

Diagnosis of Dentine Hypersensitivity will be made by obtaining detailed dental history and clinical examination of the patients prior to include in the study. History and clinical examination will eliminate and exclude the other forms and causes of Dentine Hypersensitivity which will not meet the inclusion criteria of this study. Definitive diagnosis of Dentine Hypersensitivity will be made by using Evaporative or Air blast stimulus from triple dental syringe on the sensitive surface. Then participants will be allocated to two groups through sealed envelope method. Groups will be named as Group A (Propolis) and Group B (Dentine Bonding Agent). It will only be disclosed out at the time of application of desensitizing agents by Operator.

2.7 Data Collection Procedure:

After explanation of the procedure, efficacy and safety of the materials used, possibilities of receiving either treatment options that is Propolis or Dentine Bonding Agent, the patients will be asked to sign a consent form at first (Appendix I & II). After the consent, a complete history will be obtained from the patient regarding his systemic health, medications, dental treatment and hygiene habits and smoking (Appendix III).

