At baseline (Day 0), thorough oral prophylaxis will be done for all the patients which include Scaling & Root Debridement with Polishing and detailed oral hygiene instructions should be given. Scaling is recommended to remove plaque, calculus and food remnants so clean tooth surface will be available for application of Propolis and Dentine Bonding Agent. Subjects will be provided with kit containing same type of standard Toothpaste (Colgate[®] Maximum Cavity protection PLUS Sugar Acid Neutralizer[™]) and Toothbrush (Colgate[®] 360[°] Sensitive Pro-Relief[™]) for oral hygiene during research time. Proper tooth brushing technique will be explained and demonstrated to each and every patient. Dietary counseling will also be done in order to avoid intake of excessive acids during study period.

After debridement, pretreatment assessment will be done by trained examiner. To evaluate and assess Dentin Hypersensitivity, Evaporative stimulus (controlled air blast stimulus) will be used from dental triple syringe or air water syringe which will be directed onto the affected area from a distance of 10mm for up to two seconds with complete isolation of the adjacent teeth by cotton roll. Responses will be measured on 10 cm line on Visual Analog Scale (VAS)⁵² which will be scored as 0 (No Pain), 1-3 (Mild Pain), 4-6 (Moderate Pain) and 7-10 (Severe Pain). Another scale names Schiff Cold Air Sensitivity Scale⁴⁹ will be used to measure response graded as 0, 1,

2, 3. Responses from all patients will be recorded by a single examiner, who will be blind to the applied desensitizing agents.

The patients will be allocated in to two respected groups, according to randomization by the process of sealed envelopes. The groups will be divided according to the desensitizing agents. Group A includes patients that will receive Propolis as a treating agent. Propolis obtained from Margalla hills, Islamabad by NARC (National Agriculture Research Council, Islamabad). Plant source origin is *Acacia modesta* and *Apis mellifera* bees collect it. The 30% ethanolic extract of Propolis from raw Propolis will be obtained in Pakistan Council of Scientific & Industrial Research (PCSIR) by dissolving the Propolis in 95% Ethanol and straining out the precipitate. Group B includes patients that will receive Dentine Bonding Agent (Scotchbond™ Universal Adhesive, 3M ESPE Dental Products, St. Paul, MN, USA).

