Only the Principal Investigator will be blind to the intervention given to the participants. Application of desensitizing agents to participants will be carried out by trained and experienced operator and it will only be disclosed to operator at the time of application. Operator will inform the participant about the intervention before applying and patients will not be blinded. Desensitizing agents will be applied on day 0 (baseline). Complete isolation of proximal sides from hypersensitive teeth will be done by using cotton rolls. Hypersensitive teeth surfaces will be dried by cotton pellets. Propolis will then be applied by brush on sensitive surfaces and left undisturbed for 60 seconds to let it dry. Application of Dentine Bonding Agent on sensitive surfaces will be applied single coated for 20 seconds, gently apply air for 5 seconds and cure for 10 seconds (as manufacturer's instructions). For Score 4-6 s(Moderate Pain) & 7-10 (Severe Pain) on VAS and grade 3 (Subject responds to air stimulus, considers stimulus to be painful and requests discontinuation of stimulus) of Schiff Cold Air Sensitivity Scale, application of Propolis

and Dentine Bonding Agent will be applied under Local Anesthesia and response will be recorded on next day.

Care should be taken to ensure that none of the products will touch other areas of oral mucosa. Patients will be instructed not to rinse, drink or eat for half an hour after the application of treatment agents and avoid using any desensitizing dentifrices during the course of investigation.

The clinical evaluation of Dentin Hypersensitivity will be done before and after the application of Desensitizing agents at baseline (Day 0), and also on day of re-assessment at 7th, 15th and 30th day (Appendix III).

2.8 Data Analysis:

2.8.1 Study Variables:

Independent Variables:

- Sessions (Days)
- Groups

Dependent Variables:

- Visual Analog Scale (VAS)
- Schiff Cold Air Sensitivity Scale

2.8.2 Statistical Analyses:

Statistical Package for Social Sciences (SPSS) version 20 will be used to analyze the data. The level of statically significance will be set at $p < 0.05$. to see the comparison within groups, Friedman test will be applied. For Pairwise comparison, Wilcoxon Signed Ranked Test will be used. For between groups comparison, Mann- Whitney U- Test will be applied.

2.9 Ethical considerations:

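### A within-group fall from the post-debridement baseline cannot be credited to either agent, so section 2.8.2 should rest the conclusion on the between-group comparison alone

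*Combined protocol and SAP*

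**What the plan says.** - **Debridement comes first (section 2.7).** On Day 0, "thorough oral prophylaxis will be done for all the patients which include Scaling & Root Debridement with Polishing". The first recorded score follows it: "After debridement, pretreatment assessment will be done by trained examiner". The agent is applied the same day.
- **The protocol's view of debridement (section 1.1).** Among the causes of the condition it states that "periodontal procedures (specially Scaling and Root planing) lead to dentine exposure".
- **An earlier stimulus is given but not scored (section 2.6).** "Definitive diagnosis of Dentine Hypersensitivity will be made by using Evaporative or Air blast stimulus from triple dental syringe". The data form starts at Day 0 before application, so it has no row for sensitivity before scaling.
- **No inert arm.** Section 2.6 allocates patients to propolis or to dentine bonding agent. Section 2.7 gives everyone the same toothpaste and brush, brushing instruction and diet advice.
- **Patients know their treatment (section 2.7).** "Operator will inform the participant about the intervention before applying and patients will not be blinded". Only the examiner is blind.
- **Analysis (section 2.8.2).** "to see the comparison within groups, Friedman test will be applied". Wilcoxon signed-rank follows for pairs of visits and Mann-Whitney for the comparison between groups, all at p < 0.05. The section does not say which result carries the conclusion.
- **Question asked (sections 1.5 and 1.6).** The objective and the null hypothesis concern the difference between the two agents.

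**The concern.** A test of change within one arm asks whether scores fell, not why. Here there are at least five possible reasons: the agent, settling after debridement, the hygiene and diet measures, regression to the mean in patients selected because they responded to an air blast, and expectation in patients who know what they received. No arm separates the first from the rest.

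What is at stake is the conclusion. If Mann-Whitney is not significant but both arms show a significant fall, it is natural to report that both agents are effective. The design cannot tell that outcome from one in which neither agent works. Nothing in section 2.8.2 guards against this reading. The sample size in section 2.5 is itself calculated for paired means, which leaves the role of the within-group tests less clear still.

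**Working it through.** **1. The plan's own figure.** Section 2.5 gives 5 patients per group from a test of paired means. Read as two-sided alpha 0.01 and power 0.99, with difference 1.8 and SD 0.42:
- noncentrality = (1.8 / 0.42) × √5 = 9.58; critical t on 4 df = 4.604; power = 0.9955
- with n = 4, power = 0.893

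The 5 is reproduced, although other readings of alpha and power also give values between 3 and 5. The 0.42 is 3.35 − 2.93, a difference between two SDs, so it is not used below as the SD of change.

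**2. Chance of a significant fall when neither agent works.** Inputs:
- n = 25 per arm (section 2.5) and alpha 0.05 (section 2.8.2); two-sided is assumed
- non-specific fall of 0.5, 1 or 2 VAS points: assumed, not in the documents
- SD of change of 2.0 or 2.5: assumed. Also 2.93 and 3.35, the only SDs printed (section 2.5); treating them as SDs of change is an assumption too

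For a paired t-test, power = P(T > 2.064), where T is noncentral t on 24 df with noncentrality (fall / SD) × √25. Example: fall 1.0 and SD 2.5 give (1.0 / 2.5) × 5 = 2.0 and power 0.48. Simulating the planned Wilcoxon test at the same setting (8,000 arms, normal changes) gives 46%.

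Wilcoxon results per arm follow. The chance that both arms are significant is in brackets; it is the square, since the arms are independent once the fall is fixed.

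| Fall | SD 2.0 | SD 2.5 | SD 2.93 | SD 3.35 |
|---|---|---|---|---|
| 0.5 | 21% (4%) | 15% (2%) | 12% (1%) | 10% (1%) |
| 1.0 | 65% (43%) | 46% (21%) | 36% (13%) | 29% (8%) |
| 2.0 | >99% (99%) | 96% (93%) | 89% (79%) | 80% (64%) |

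With no non-specific fall, a significant fall appears in 2–3% of arms, as it should.

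**3. The between-group test.** A fall common to both arms shifts both by the same amount and leaves their difference unchanged. In a simulation of five readings per patient on a 0–10 scale, with shared falls from 0 to 3 points and no agent effect, Mann-Whitney at Day 30 was significant in 3.8–5.8% of trials. This covers shared influences only. Expectation that differs between the two named agents would not cancel.

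**4. Which readings are affected.** Settling after debridement can act on Days 7, 15 and 30. It hardly explains a fall immediately after application, where expectation matters more. For higher scores, section 2.7 also calls for local anaesthesia and a response recorded the next day, while the form has only a row for immediately after application. Those passages must be reconciled before the immediate reading can be interpreted.

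**The case against.** The strongest case on the other side has four parts.

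- **The question is between groups.** A trial with two active arms is legitimate for it, and no passage promises a claim for each agent from the within-group tests. This stands. It limits the point to interpretation, but section 2.8.2 still tests within-group change for significance without saying what those results are for.
- **The size is unknown.** A reader might infer that the within-group tests are bound to show significant falls. The documents do not support that: they give neither the non-specific fall nor the SD of change, and at the low end of the table the chance is only about 10%.
- **The effect of debridement on the score is inferred.** A reader might also infer that the baseline is taken within minutes, is raised, and is a noisier measure of usual sensitivity. The text says only that it follows debridement on Day 0. It speaks of dentine exposure, not of a temporary rise that settles by Day 30. Entry is limited to plaque Score I, and calculus Scores 2 and 3 are excluded, which may limit how much debridement is needed. This stands, so settling is one possible component among several.
- **Scoring after scaling has a logic.** It keeps the effect of scaling itself out of the contrast before and after the agent. The air blast in section 2.6 is the eligibility reading, so change measured from it would be more exposed to regression to the mean. This also stands, and it is why a pre-scaling score is only optional below.

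None of this removes the attribution problem, which exists whatever the size of the fall because there is no concurrent inert control.

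**Conclusion.** The concern holds as a limit on what the within-group tests can show. A significant Friedman or Wilcoxon result in either arm, or in both, is not evidence that the agent works. Under the assumed falls of 0.5 to 2 points and SDs of change of 2.0 to 3.35, an arm of 25 would show such a result in roughly 10% to 99% of trials with no agent effect. The width of that range reflects inputs the documents do not supply; the attribution point does not depend on it.

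A reader might go further and infer that the randomised comparison is compromised as well. The documents do not support that on this ground: debridement, hygiene kit and diet advice are common to both arms, and a shared fall leaves the type I error at about 5%.

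**What to change.** In section 2.8.2:

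1. State that the conclusion rests only on the comparison between the randomised groups, and that Friedman and Wilcoxon results are descriptive. State also that no claim that either agent works on its own will be drawn from them, including a claim that both are effective after a non-significant between-group result.
2. Adjust the between-group comparison for the Day 0 pre-application score, for example by ANCOVA or rank ANCOVA in place of the unadjusted Mann-Whitney test, which takes no covariate. The score is already collected, before the agent is applied and before the patient is told which agent it is.
3. Optionally, record VAS and Schiff before scaling, after consent, with the same standardised stimulus that section 2.7 specifies (10 mm, up to two seconds, adjacent teeth isolated). Use it only as an additional covariate and a descriptive reading, not as the main reference for within-group change.

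Items 1 and 2 cost a few sentences and a small amount of modelling. Item 3 adds a row to the form and has to be decided before enrolment, because the score cannot be recovered later. The real cost is that the study gives up any claim that each agent works on its own; that claim would need a concurrent inert control.

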In this six month In- Vivo single blinded Randomized Clinical Study, a total number of 50 patients with complain of dentine hypersensitivity will be selected in two groups after taking consent. Group A and B will receive Propolis and Dentine Bonding Agent respectively by a trained operator. Recordings of Dentin Hypersensitivity will be obtained at Day 0, before and after the application of experimental agents, and also on Day 7, 15 and 30 by the Researcher. Response will be measured by Visual Analog Scale and Schiff Cold Air Sensitivity Scale. SPSS v.20 will used to analyze the data with level of significance set at $p < 0.05$. Friedman test will be applied to see the comparison within groups and Wilcoxon Signed Rank test will be used for Pairwise comparison. Mann Whitney U-Test will be applied for comparison between groups.

Key Words: Dentin Hypersensitivity, Propolis, Dentine Bonding Agent, Visual Analog Scale (VAS), Randomized Clinical Trail, Schiff Cold Air Sensitivity Scale

CHAPTER 1: INTRODUCTION

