1.5 Objectives

The objective of this study is to explore which is more effective between Propolis and Seventh generation Dentine Bonding Agent for the treatment of Dentine Hypersensitivity.

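### Section 2.7 has the operator name the agent to each patient although both outcomes rest on the patient's own response; not naming it is a cheap improvement with a possibly small gain

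*Combined protocol and SAP*

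**What the plan says.** Section 2.7 explains the study to patients before they sign consent, and the explanation covers both possible treatments: "After explanation of the procedure, efficacy and safety of the materials used". The envelope allocation is kept from the operator until the last moment: "it will only be disclosed to operator at the time of application". The operator then passes it on: "Operator will inform the participant about the intervention before applying and patients will not be blinded".

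The applications differ. Propolis is brushed on and "left undisturbed for 60 seconds to let it dry". For the bonding agent the steps after the 20-second coat are "gently apply air for 5 seconds and cure for 10 seconds".

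A single blinded examiner records the responses. The Abstract has the follow-up recordings taken "and also on Day 7, 15 and 30 by the Researcher", and 2.7 limits blinding to the principal investigator. The Abstract and section 2.1 call the trial single blinded.

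Section 2.8.1 lists two dependent variables. VAS is marked on a 10 cm line, and section 1.7 defines it as an instrument for subjective characteristics. Schiff is graded by whether the subject reacts, asks for the air to stop, or finds it painful (section 1.7 and the recording form).

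The aim in section 1.5 is to "explore which is more effective between Propolis and Seventh generation Dentine Bonding Agent". Section 2.8.2 gives one between-group method: "For between groups comparison, Mann- Whitney U- Test will be applied".

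**The concern.** A blinded examiner protects how a response is written down, but not the response itself. Both scales start from what the patient feels, reports or asks for. A patient who knows the agent, and expects more or less of it, can carry that expectation into either score.

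If expectations differ between the arms, the difference enters the Mann-Whitney comparison and cannot be told apart from a treatment difference. Expectation is not measured, so no later analysis can recover it. Up to 8 between-group tests could be touched (2 scales × 4 post-application readings: Day 0 after application, Days 7, 15 and 30). The plan does not say which readings are compared.

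The visible text gives no reason for naming the agent, and no described procedure depends on it. A secondary point, on which the concern does not rest, is that a patient who has been told the name can repeat it to the examiner at any later visit. The text we have describes no safeguard against that, although the consent pages are not in our copy.

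**Working it through.** **Figures in the plan.** The plan gives no figure for expectation bias, so there is none to reproduce. The 25 per group in section 2.5 is taken as given.

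**Inputs from the plan.** 25 patients per group (2.5); significance level 0.05 (2.8.2), taken as two-sided; SDs of 2.93 and 3.35 (2.5). The SDs are cited there for degree of sensitivity with no scale stated. Applying them to VAS is an assumption.

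**Assumed quantities, not given in the plan.** D is the shift in VAS between arms, due to expectation alone, when every patient knows the agent. r is the share of patients who would recognise the agent without being told. Only patients who know the agent carry the shift, and there is no true treatment difference. Naming sets r to 100%.

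**Closed-form check (two-sample t).** The mean shift is r × D. The noncentrality is (r × D / SD) × √(25/2), with 48 degrees of freedom. For D = 0.5, SD = 2.93, r = 1 this is (0.5/2.93) × 3.536 = 0.603, and the two-sided rejection rate is 9.1%.

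| D | SD | r = 100% (named) | r = 90% | r = 75% | r = 50% |
|---|---|---|---|---|---|
| 0.5 | 2.93 | 9.1% | 8.3% | 7.3% | 6.0% |
| 0.5 | 3.35 | 8.1% | 7.5% | 6.7% | 5.8% |
| 1.0 | 2.93 | 21.9% | 18.7% | 14.4% | 9.1% |
| 1.0 | 3.35 | 17.9% | 15.4% | 12.1% | 8.1% |

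**Planned test (Mann-Whitney on VAS).** Simulated with 20,000 replicates, patient-level mixture, Monte Carlo standard error at most 0.3 point. With D = 0 the rate is 4.7-4.8%.

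| D | SD | r = 100% (named) | r = 90% | r = 75% | r = 50% |
|---|---|---|---|---|---|
| 0.5 | 2.93 | 8.8% | 8.2% | 6.9% | 5.6% |
| 0.5 | 3.35 | 7.9% | 7.4% | 6.6% | 5.6% |
| 1.0 | 2.93 | 20.8% | 17.8% | 13.7% | 8.8% |
| 1.0 | 3.35 | 16.8% | 14.7% | 11.9% | 8.1% |

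Limiting scores to the 0-10 range changes these rates by up to about 0.15 point.

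**Part due to naming (named column minus the others, Mann-Whitney).**
- D = 0.5: from 7.9 − 7.4 = 0.5 to 8.8 − 5.6 = 3.2 points.
- D = 1.0: from 16.8 − 14.7 = 2.1 to 20.8 − 8.8 = 12.0 points.

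**High recognition.** At r = 95% the closed-form model gives a naming effect of 0.3-0.4 point (D = 0.5) or 1.3-1.7 points (D = 1.0). At r = 100%, or with D = 0, it is zero.

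**The case against.** The strongest reply is that naming adds little to what patients will work out for themselves. They hear the procedure and both options before consent. Only one arm has a light cure, and with two options a patient who recognises one step can identify either agent by elimination. Recognition above 90% is plausible, and there the effect of naming is small. This stands: the documents do not show how many patients would recognise the agent, and the gain may be nil.

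Sections 1.2 and 1.3 also present both agents as effective, so expectations may be equal and the net bias near zero. This stands too.

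The consent pages are not in our copy, so it cannot be checked whether patients must be told which agent they receive. For that reason the risk should not be called avoidable, and any change is conditional on the ethics committee.

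A reader might infer more than the documents support:
- *The single-blind label is wrong.* It is not. The plan says openly that patients are not blinded and that the examiner is.
- *The disclosure rule contradicts the instruction to inform the patient.* It need not. The rule can be read as fixing when the operator learns the allocation, and the next sentence has the operator pass it on.
- *The trial's comparison is biased.* Nothing in the documents shows that patients expect more of one agent, so neither a bias nor its direction is established.

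**Conclusion.** The point holds as a low-cost improvement to the design. No analysis error is claimed. Naming the agent makes knowledge of it certain for all 50 patients, on outcomes where examiner blinding cannot protect against expectation.

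The percentages in the working show how sensitive the planned test would be to shifts of 0.5 or 1.0. They do not estimate the bias present, nor the bias that would be removed. They rest on assumed values of D and r and on SDs borrowed from an unstated scale. The case for the change rests on its small cost. The within-group Friedman and Wilcoxon tests are not part of this point.

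**What to change.** In 2.7, replace the instruction to inform the participant with: *The operator will apply the assigned agent without naming it to the participant.*

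Align the surrounding text:
- In 2.6, say that the allocation is disclosed to the operator only. The present wording can be read as the operator disclosing it at application.
- In 2.7, replace the statements that only the principal investigator is blind and that patients are not. Say instead that the examiner is blinded and the agent is not named to patients, whose masking may be incomplete.
- Keep the label, as single blinded (examiner).

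Subject to ethics committee agreement and the consent wording, tell patients at consent that the agent will be disclosed after the Day 30 scores, or earlier on withdrawal or if they need to know. Someone other than the examiner should disclose it. Ask patients not to discuss the application with the examiner.

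Optionally, after the Day 30 scores, collect a sealed guess of the agent, with a do-not-know option, kept from the examiner. Report it by group as description only. It cannot prove that masking worked: 12 of 25 correct has a 95% Wilson interval of 30-67%. State incomplete patient masking as a limitation.

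The cost is a few sentences in 2.6 and 2.7, consent wording, and a disclosure step for each patient (plus a slip if guesses are collected). Sample size, treatments, visits and tests stay as they are. The downside is that the effort may bring little gain.
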